15.2 Coded Terms for Adverse Events of Special Interest

The AESIs of Anaemia and Hypothyroidism will be programmatically identified using the following MedDRA preferred term codes;

Hypothyroidism

- 10036697 . 10018096
 - 10043693
- 10021114
 - 10059844 •
- 10076644 10078564 •

10065306

- 10087712 • 10083075 10087924
- 10028665 10060819 •

Anaemia

- Anaemia macrocytic (10002064)
- Aplasia pure red cell (10002965)
- Aplastic anaemia (10002967) •
- Erythroblast count decreased (10058505) •
- Erythroid maturation arrest (10015279) •
- Erythropenia (10015287) •

- Hypoplastic anaemia (10021074) ٠
- Microcytic anaemia (10027538)
- Proerythroblast count decreased (10060229) •

10086754

10087670

- Red blood cell count decreased (10038153) •
- Reticulocyte count decreased (10038790) •
- Reticulocytopenia (10038795) •

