7.1.4 Clinical Laboratory Abnormalities and Other Abnormal Assessments

Laboratory abnormalities without clinical significance should not be recorded as AEs or SAEs. However, laboratory abnormalities as per the investigator's assessment (eg, clinical chemistry, haematology, and urinalysis abnormalities) that require medical or surgical intervention or lead to IMP interruption, modification, or discontinuation must be recorded as an AE or SAE, as applicable. In addition, laboratory or other abnormal assessments (eg, in ECGs, X-rays, or vital signs) that are associated with signs and/or symptoms must be recorded as an AE or SAE if they meet the definition of an AE or SAE as described in Sections 7.1 and 7.1.2. Any worsening of existing abnormalities that are associated with signs and/or symptoms (except for SCCHN-related pre-existing conditions, including disease progression [see Section 7.3]) should be reported as AEs or SAEs, as appropriate. If the laboratory abnormality is part of a syndrome, record the syndrome or diagnosis (eg, anaemia), not the laboratory result (ie, decreased haemoglobin).

For specific information on handling of clinical laboratory abnormalities, see Section 5.3.2.

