7.1.5 Adverse Events of Special Interest

The AESIs for this study are anaemia and hypothyroidism.

AESIs of anaemia will be defined as CTCAE Grade ≥ 3 anaemia. Please refer to Section 5.3.2.1 for details regarding the detection and management of potential cases of anaemia.

AESIs of hypothyroidism will be defined as TSH levels of ≥ 10 mIU/L. AESI will be unconfirmed with only one test. Please refer to Section 5.3.2.2 for details regarding the detection and management of hypothyroidism.

The AESI should be reported by the investigative site to the ICON Drug Safety Centre within 24 hours of learning about the event by completing the paper safety report form and sending it via email or fax. The documentation and processing of AESIs is further detailed in the investigator site file.

Investigators will indicate on the relevant Adverse Event eCRF page if the event meets the criteria for an AESI.

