10.10.5 AESIs

AESIs will be programmatically identified using the MedDRA codes provided in Section 15.2.

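### The SAP identifies adverse events of special interest by MedDRA code alone, without the protocol's CTCAE Grade ≥3, TSH ≥10 mIU/L or eCRF-flag conditions, and does not declare the change

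*SAP*

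**What the plan says.** Protocol 7.1.5 defines the two AESIs by criteria. For the first, "AESIs of anaemia will be defined as CTCAE Grade" ≥3 anaemia. For the second, "AESIs of hypothyroidism will be defined as TSH levels of" ≥10 mIU/L, with the qualification that an "AESI will be unconfirmed with only one test". The same section provides a data source: "Investigators will indicate on the relevant Adverse Event eCRF page if the event meets the criteria for an AESI".

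The SAP uses a different rule. Section 10.10.5 is one sentence: "AESIs will be programmatically identified using the MedDRA codes provided in Section 15.2". Section 15.2 opens with "The AESIs of Anaemia and Hypothyroidism will be programmatically identified using the following MedDRA preferred term codes" and then gives the list. SAP 12.6.1 reports AESIs as a line in the overall TEAE summary, with a cross-reference to 10.10.5, and again in a table by system organ class and preferred term.

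SAP 7.2 names AESIs of anaemia and hypothyroidism within the secondary safety endpoint. SAP 6.1 sets out major changes, minor changes and clarifications relative to the protocol. It covers points as small as how concentrations below the quantification limit are treated, but does not mention the AESI definition.

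**The concern.** A preferred-term code says what kind of event was recorded. It does not say whether the event reached Grade 3 or whether TSH reached 10 mIU/L. Selecting on the code alone therefore yields a different set of events from the one the protocol defines, and the two can differ in both directions.

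The AESI table would then not match the AESIs that sites report under Protocol 5.3.2.1, 5.3.2.2 and 7.1.5. A reader of the study report would have no warning, since SAP 6.1 is silent. Protocol 1.3 (Table 2) singles out haematological and thyroid effects as risks suggested by the canine studies, so these are the two safety topics a reader is most likely to look up in the AESI table.

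**Working it through.** No sample size, alpha or power figure is involved. The check compares the rules and then counts the list.

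**Step 1. The two rules side by side.**

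| Element | Protocol 7.1.5 (v4.0) | SAP 10.10.5 and 15.2 |
|---|---|---|
| Anaemia severity | CTCAE Grade ≥3 | No condition |
| Hypothyroidism threshold | TSH ≥10 mIU/L | No condition |
| Investigator flag on the AE eCRF page | Records whether the criteria are met | Not used |
| Preferred-term list | None | The only selector |

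The flag is not itself a criterion; it is the site's record that the criteria were met. In SAP 12.6.1 the line for severe TEAEs carries a written Grade ≥3 limit and the AESI line carries none, so a grade limit cannot be read into the AESI line by default.

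**Step 2. How the counts differ.** Let A be the patients with an event under a listed code but none meeting the protocol definition. Let B be the patients with a qualifying event but none under a listed code. Then, for each arm:

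SAP count − protocol count = A − B.

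A runs from 0 to all patients whose only listed-term events fail the protocol criteria (for anaemia, Grade 1–2 only). B runs from 0 to all patients whose only qualifying events are coded outside the list. The documents give neither a Grade ≥3 anaemia rate nor a coding split, so neither number can be fixed. If A and B were of similar size the totals would agree while the patients counted would not be the same.

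**Step 3. The list in SAP 15.2, in the copy read.**
- Under hypothyroidism: 13 codes, none with a name.
- Under anaemia: 12 named terms and 2 bare codes (10086754 and 10087670).
- Total: 13 + 12 + 2 = 27 entries, all distinct. Entries carrying a grade, TSH or flag condition: 0.
- Named anaemia terms that are plain Anaemia: 0 of 12.
- Named anaemia terms that are 'count decreased' laboratory terms: 4 of 12 (erythroblast, proerythroblast, red blood cell, reticulocyte).

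**Step 4. Why the absent term would matter.** Where a laboratory abnormality is part of a syndrome, Protocol 7.1.4 tells sites to "record the syndrome or diagnosis (eg, anaemia), not the laboratory result (ie, decreased haemoglobin". Its example is the very word that does not appear on the list. If plain Anaemia really is missing, a Grade ≥3 event recorded as instructed could fall outside the AESI table.

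**Step 5. Hypothyroidism.** A TSH ≥10 mIU/L leads to interruption of IMP under Protocol 5.3.2.2, and Protocol 7.1.4 says that laboratory abnormalities that "lead to IMP interruption, modification, or discontinuation must be recorded as an AE or SAE". An AE record should therefore exist. What remains uncertain is whether that AE is coded to one of the 13 unnamed codes, and whether AEs under those codes had TSH below 10 mIU/L. SAP 12.6.3 plans TSH summaries by visit, box plots and out-of-range flags, but no count of patients at the protocol threshold.

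**The case against.** **The protocol supplied is not the one the SAP used.** SAP 6.0 cites protocol v5.0 and CRF v5.0; the protocol supplied is v4.0. Section 7.1.5 or the flag may have changed. This stands as a condition on the finding and makes verification the first step.

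**The list is damaged in the copy read.** Bullets are displaced and two bare codes sit inside the anaemia block. Every other anaemia entry has a name, so these two look like displaced hypothyroidism codes, but that cannot be confirmed. This stands: the absence of plain Anaemia is a query for the original page. The main point does not depend on it, because the sentence in SAP 10.10.5 is intact.

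**The list may be deliberate.** Many of the named terms concern aplasia, hypoplasia or low red-cell-lineage counts, which resembles the canine finding in Protocol 1.3, Table 2. A targeted search would be legitimate. It would still be a departure from Protocol 7.1.5, and the SAP neither declares it nor gives a reason.

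**The information is mostly shown elsewhere.** SAP 12.6.1 tabulates all TEAEs by preferred term and maximum severity, and Grade ≥3 TEAEs by preferred term. SAP 12.6.3 adds laboratory summaries and CTCAE shift tables. Safety is descriptive under SAP 12.6. The endpoint tables in both documents name anaemia and hypothyroidism without a grade, and nothing supplied requires the AESI table to reconcile with expedited site reports. All of this stands and limits the consequence. It does not make the AESI table agree with the protocol's definition.

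The TFL shells were not available. SAP 12.0 says they hold presentation details, whereas the selection rule itself is in 10.10.5.

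**Conclusion.** The concern holds. On intact text, SAP 10.10.5 and 15.2 select AESIs by code only, Protocol 7.1.5 (v4.0) defines them by grade and TSH with an investigator flag, and SAP 6.1 does not declare the difference. The AESI line and the AESI table would therefore hold a different set of events from the protocol's. The size of the difference is unknown; the bounds in step 2 are all that the documents allow.

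Three stronger readings are tempting and are not supported:

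- A reader might infer that severe anaemia would disappear from the study report. It would not: the Grade ≥3 TEAE table would still show a Grade ≥3 TEAE by arm under whatever term it was coded to.
- A reader might infer that plain Anaemia was certainly left out. The damaged layout does not allow that conclusion.
- A reader might infer that hypothyroidism will be undercounted. The 13 codes have no names, so their coverage cannot be judged either way.

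The finding assumes that Protocol 7.1.5 was not materially changed in v5.0 and that the TFL shells add no grade, TSH or flag condition. The consequence is confined to descriptive AESI outputs. It is worth correcting because the correction is cheap and AESIs are part of a named secondary safety endpoint.

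**What to change.** 1. Check the AESI definition against protocol v5.0, the AESI flag against CRF v5.0, and the SAP 15.2 list against the original page, in particular whether plain Anaemia and the two bare codes belong to it.
2. Rewrite SAP 10.10.5 so that AESIs follow the protocol criteria. Use the eCRF AESI flag as the primary source. Add AEs with anaemia-type terms at CTCAE Grade ≥3, including plain Anaemia if it is confirmed absent from the list.
3. Report the number of patients per arm with any recorded post-baseline TSH ≥10 mIU/L. The label should say that this rests on recorded values: Protocol 5.3.2 generally keeps local results out of the eCRF, though it allows results of the anaemia and hypothyroidism retests to be requested when central confirmation is not possible.
4. Keep the preferred-term list as a supplementary display and print the names of the hypothyroidism terms.
5. If a targeted list is intended as the main definition, say so in SAP 6.1 with the reason.

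The cost is SAP wording, a revised derivation and one added laboratory count. CTCAE grade and central-laboratory TSH are already planned data; the flag is described in Protocol 7.1.5 and only its presence in CRF v5.0 needs confirming. No additional patient assessments are needed.
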